## Specific Aim #2: To determine whether adjunctive ketamine is associated with opiate sparing.

This will be measured by documenting each participant's number of Requests for Additional Analgesic Medications (i.e., RAAMs) for acute nociceptive pain during each of the 14 wound care procedures from Day 1 to Day 7 of the Trial.

**The seven secondary outcome measures** of the proposal are: 1) Rates of acute and posttraumatic stress disorder (i.e., ASD and PTSD); 2) Rates of major depressive disorder; 3) Sleep quality and duration; 4) Pain-related anxiety; 5) Catastrophizing; 6) Emotion Regulation and; 7) Trauma resilience.

1) ASD and PTSD will be assessed using the Diagnostic and Statistical Manual of Mental Disorders V-(DSM V). By definition, to meet criteria for PTSD, symptoms must be present for 1 month. As such, prior to the 1-month post-injury time-point, subjects with symptoms consistent with PTSD related to their burn injury will be diagnosed with ASD, rather than PTSD. It is hypothesized that subjects in the K + UC group will have a lower percentage of patients who meet criteria for PTSD, when compared to subjects in the UC group. It is also hypothesized that a number of factors will moderate the presence and severity of ASD and PTSD; these include:

a) Pain, as measured above. Mutual Maintenance Theory: We anticipate that "mean pain" of all 14 sessions (i.e., group average of all observations across all 14 sessions) and the trajectory of pain through the 14 sessions (i.e., group X individual trajectory within session, and, group X individual trajectory across all 14 sessions) will be predictive of PTSD development and PTSD symptom severity at 1-month.

b) Sympathetic reactivity (as measured above). We expect that greater sympathetic reactivity during the wound care procedures will be associated with ASD and PTSD.

c) Depressive symptom severity as measured using the Beck Depression Inventory (BDI-II) during the week of wound care, and at the 1-month time-point.

d) Sleep during the night following wound procedures (measured by both self-report and with the Itamar Watch-PAT200) and at the 1-month time point (self-report).

e) Trauma Resilience (as measured using the Trauma Resilience Scale: Trait- at baseline, and at 1-month time-point).

f) Distress at baseline in reporting the burn event (as measured by self-report and the Itamar Watch-PAT200)

g) Optimism (as measured by the Life Orientation Test: Trait – baseline)

h) Emotion Regulation (as measured by the Emotion Regulation Scale-State: baseline and post-procedure)

**2) Major Depressive Disorder**: It is hypothesized that subjects in the K + UC group will have significantly lower rates of major depressive disorder, as defined by the DSM V and Beck Depression Inventory-II, than subjects in the UC condition. It is anticipated that the same factors that are hypothesized to moderate ASD and PTSD (see above) will moderate major depressive disorder. Further, we anticipate that severity of ASD and PTSD will be predictive of severity of major depressive disorder.

**3) Sleep:** Sleep will be assessed by the Itamar Watch-PAT 200, and by self-report (Insomnia Severity Index, and, Sleep-Pain Diary). It is hypothesized that subjects in the K+UC group will have superior sleep to those in the UC group. The same factors that are hypothesized to moderate PTSD and depression are anticipated to moderate sleep quality.

**4) Pain Anxiety Symptom Scale-20** (Kleiman, 2011) will be used to test the hypothesis that the K+UC condition, when compared to the UC condition will result in significantly fewer symptoms of pain-related anxiety at 1-month follow-up. Similarly, these measures will be used to test the hypothesis that pain anxiety assessed within 1 hour prior to start of Sessions 1, 5 and 7 will moderate the effect of Study Drug on measures of acute pain. Finally, this measure will be used to test the hypothesis that change in pain anxiety will moderate the effect of study drug on change in PTSD symptoms and PTSD diagnosis.

**5) Catastrophizing:** Pain-related catastrophizing will be measured using the Pain Catastrophizing Scale (PCS; Sullivan, 1995) which was developed to assess three components of catastrophizing: rumination, magnification, and helplessness. It is hypothesized that the K+UC condition, when compared to the UC condition will result in significantly fewer symptoms of pain-related catastrophizing at 1-month follow-up. It is also hypothesized that pain-related catastrophizing assessed within 1 hour prior to start of Day 1 (Session 1), Day 4 (Session 7) and Day 7 (Session 13) will moderate the effect of Study Drug on measures of acute pain (across all 7 days and 14 sessions, as well as during Sessions 1, 7 and 13 respectively).

**6) Emotion Regulation:** Emotion regulation will be measured using the Emotion Regulation Scale (ERS: Spaapen, Waters, Brummer, Stopa, Bucks, 2014) and will test the hypothesis that emotion regulation will moderate the effect of pain anxiety and pain catastrophizing on pain, opiate sparing, PTSD, and depression symptom severity at 1-month follow-up.

**7) Trauma Resilience:** We will use the Connor-Davidson Resilience Scale (CD-RISC: 2007) to measure resilience to test the hypothesis that trauma resilience will moderate the effect of pain anxiety and pain catastrophizing on acute pain, opiate sparing, PTSD, and depression symptom severity at 1-month follow-up.

**3. Background** (briefly describe pre-clinical and clinical data, current experience with procedures, drug or device, and any other relevant information to justify the research)

There is a need for high-grade evidence supporting the optimal drug, dose, route and duration of analgesia to be used in combat and other austere conditions. The greatest need is to identify medications with superior benefits (rapid onset, adequate pain relief, retained physical and physical function) and fewer side effects (impaired cognition, respiratory suppression, reduced physical function) than are observed with the use of standard opiate-based pain medications.

One unfortunate, yet essential characteristic of wound care for deep burns, as well as for many traumatic injuries, is the debridement / wound cleansing / dressing change procedures that occur 2-times per day until wound closure has been achieved. Burn wound debridement, cleansing, and dressing change procedures involve repeated exposure to acute nociceptive stimuli, often leading to an intensifying sensitivity of nociceptors in the wounded area (primary hyperalgesia), the area surrounding the wounded area (secondary hyperalgesia) (Myer, Ringkamp, Campbell, Raja, 2005), as well as generalized pain in areas that are remote from the wound (allodynia). (Latremoliere, 2009).

The standard practice for analgesia during acute burn care is the use of using either hydromorphone (Dilaudid) or fentanyl – in the BICU, fentanyl is by far the preferred analgesic. The choice of narcotic analgesic is determined by the preference of the Critical Care Medicine team in the Burn Intensive Care Unit. Fentanyl (Siblimaze), opiate analgesics are given intravenously. The onset time for narcotics administered intravenously is within minutes. In addition to concerns related to opiate-induced respiratory suppression, ongoing use of morphine in situations such as sustained daily burn wound care over weeks and sometimes months, can lead to the development of tolerance and opiate-induced hyperalgesia (Gupta, 2015).

Ketamine (2-(O-chlorophenyl)-2-methylamino cyclohexanone) is a non-barbiturate anesthetic/analgesic agent structurally related to phencyclidine and cyclohexamine. Ketamine is the only single-agent anesthetic capable of producing a "dissociative" anesthesia, which has been useful for a variety of outpatient and inpatient surgical procedures. This agent is also known to produce potent analgesia at sub-anesthetic therapeutic concentrations. The hypothesized opiate sparing effect of ketamine for the treatment of burn-related pain holds significant promise for treating/preventing previously mentioned untoward opiate effects.

Numerous theories have been proposed to explain the effects of ketamine, including usedependent blockade of N-methyl-d-aspartate (NMDA) receptors in the central nervous system, interactions with opiate receptors at central and spinal sites, and interaction with norepinephrine, serotonin, and muscarinic cholinergic receptors. Data suggest that some effects of ketamine may be mediated via non-opioid mechanisms. Warncke, et al., (1997) interpreted their experimental burn findings in healthy volunteers that the mechanisms underlying secondary hyperalgesia are "mediated by glutamatergic transmission via NMDA receptors." The potential advantages of using ketamine instead of narcotics and benzodiazepine drugs during austere operations include the preservation of muscle tone and protective airway reflexes, reduced risk of respiratory depression, reduced incidence of hemodynamic instability in shock, reduced need for opioids, and decreased nausea and vomiting.

Two recent randomized controlled trials (RCTs) compared the efficacy and features of ketamine versus opiates in treating pain among samples with pain related to minor trauma in an emergency department setting (Motov, 2015; Miller, 2015). Neither study found significant differences between morphine and low-dose intravenous ketamine in pain relief at 30 minutes post-infusion – that is, ketamine and morphine were equi-analgesic (Miller, 2015; Motov, 2015). Motov also noted the groups were similar in the number of patient requests for additional analgesic fentanyl at 30 or 60 minutes. Notably, however, Miller found that the mean time to maximum pain relief was much more rapid following treatment with ketamine (i.e., ketamine = 5 minutes, Morphine = 100 minutes). If this observation of abbreviated elapsed time to achieve maximum pain relief is replicated in the current study of burn wound pain, then ketamine may hold a distinct advantage over opiate medications when pain is severe and time is of the essence (e.g., combat, wound care).

In contrast to studies involving patients with trauma injuries, a recent review of the few RCTs examining ketamine in burn patients (McGuinness, 2011) found that ketamine reduced burn pain (both primary hyperalgesia and secondary hyperalgesia) significantly better than morphine. This differential efficacy of ketamine in burn pain, but not in non-burn traumatic wounds, if validated in well-designed studies among patients with acute burns, may have important implications for managing battlefield trauma- versus battlefield burn- related pain. While ketamine has been a tool in the treatment of burn patients for years, there is a dearth of well-designed trials of the safety and efficacy of ketamine in burn patients. Fewer still have studied optimal dosing, opiate-sparing potential, preferred delivery modality, patient comfort and satisfaction, impact on targets in other systems/syndromes, and mechanism of action. Many of the extant ketamine studies in patients with burn injuries involved case report or case series designs, no blinding or randomization, higher doses of ketamine, only pediatric patients, drug delivery via inhalation versus IV infusion, and small, inadequately characterized samples (McGuinness, 2011). Stated simply, there is insufficient literature to ensure the safety and efficacy to support the use of ketamine as analgesia in combat soldiers with burns, or adult civilians with burn injury sustained in austere conditions.

2. Safety and Efficacy of Low-Dose, Slow Infusion Ketamine (Pourmand, et al, 2017)

The goal of using low-dose ketamine (LDK) is to provide analgesia without producing the adverse effects that occur more frequently at higher doses. LDK has been found to be safe and effective as an analgesic with a favorable adverse effect profile. Within the studies reviewed, 1187 patients received LDK. The most common adverse effects were dizziness, nausea, vomiting, and mild neuropsychological reactions such as hallucinations or agitation (4) [25]. Almost all of these adverse effects resolved spontaneously - emergence phenomenon is unusual when low doses are used and when reported, it is mild and transient.

LDK has been shown to be safe and effective for the treatment of a wide variety of painful conditions in the ED where it is comparable to opioids in reducing pain. Respiratory suppression is less of a risk with ketamine than with high dose of IV opioids and it is effective for the management of pain exacerbations in opioid tolerant patients. Although potential for abuse is present, "ketamine has less potential for addiction or epidemic overuse" than opioids.

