#### REFERENCES

Protocol and Statistical Analysis Plan\_20171117.doc C:\Ketamine for Acute Burn Pain\[name]\HRPO Documents\1.1.A\_eformA\_01.29.2017 To 08.22.2017\_TRACK CHANGEES\_SUBMITTED Page 7 of 31

(linked numbers from original: Pourmand, et al., 2017)

1. [16] A.B. Petrenko, T. Yamakura, K. Sakimura, H. Baba. **Defining the role of NMDA receptors in anesthesia: are we there yet?** Eur J Pharmacol, 723 (2014), pp. 29-37

2. [17] J. Sleigh, M. Harvey, L. Voss, B. Denny. **Ketamine – more mechanisms of action than just NMDA blockade** Trends in Anaesthesia and Critical Care, 4 (2014), pp. 76-78

3. [18] A. Gupta, L.A. Devi, I. Gomes. **Potentiation of μ-opioid receptor-mediated signaling by ketamine** J Neurochem, 119 (2011), pp. 294-302

4. [25] B. Sin, T. Ternas, S.M. Motov. The use of subdissociative-dose ketamine for acute pain in the emergency department. Acad Emerg Med, 22 (2015), pp. 251-257

The risk and benefits of LDK, relative to opioid medications, were reviewed by Lee and Lee (2016). The reviewed a total of 6 trials involving 438 patients evaluating LDK in the ED. They reported that "... subgroup analysis of pain reduction indicates that the favorable effects of ketamine were similar or superior to those of placebo or opioids." While the results indicated that low-dose ketamine was associated with a higher risk of neurological (relative risk [RR] = 2.17) and psychological (RR = 13.86) events, the opioid medications had a higher risk of major cardiopulmonary events (RR = 0.22).

3. Cognitive impairment in healthy volunteers and in clinically-defined abusers of ketamine (Liu, Lin, Wu, Zhou, 2016)

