#### Summary of Medication Dose, Timing, Method:

- a. The Fentanyl loading dose will begin <1 minute prior to each wound care session for both the Usual Care and the Ketamine Augmentation groups.
- b. The drug delivery mechanism for the loading dose of ketamine / placebo, as well as all of the continuous infusions, will be via identical masked / nondescript infusion bags. The ketamine / placebo contents will be delivered at identical volumes and continued for the duration of the wound care session in order to preserve the blind.
- c. The blinded infusion bags will be used to deliver both ketamine and saline and will be prepared and provided by the JHBMC pharmacy ([name]). The pump will be programmed by the JHBC nurse based on the provider's prescription, the randomization schedule and the EPIC order set (displayed in EPIC and on infusion bag label).
- d. Wound Care Protocol and Outcome Protocol Duration:

i. Study / Follow-up Protocol: Eligibility determination (ED); consent procedures; informed consent signed (as soon as possible post-admission to the BICU); randomization; initial wound care protocol soon after consented, (1st wound care optimal); twice daily (preferred) wound care (potential range 0-2 sessions daily: there may be days on which no wound care is performed for various reasons such as dressing type, post op, etc) protocol for 7 consecutive days (potential range 3-7 days); Follow-up 1 day, 1-week and 1-month after last of the 7-day study protocol for a total of 5 weeks or n= 35 days per participant.

ii. Wound Care Study Protocol: Includes pretest assessment, premedication (loading dose), wound care and interim infusion and assessments, posttest assessments. Each wound care procedure including assessments will take approximately 1-2 hours.

ii. Ketamine for Acute Burn Pain During Burn Wound Care Protocol: Twice daily wound care sessions, estimated length of hospitalization on BICU is ≥5 days (range = 3 - 7 days).

2. Burn Center 5-year Average population meeting Key Inclusion Criteria

[name], MSN, Trauma Coordinator, provided the speadsheets with the admissions data. [name] is Trauma Coordinator for the trauma and burns at JHBMC and maintains datasets for the Maryland Institute for Emergency Medical Services Systems (MIEMSS) and the American Burn Association (ABA) Registry and has access to all data from the JHBC entered in these systems.

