# d. Justification of why participants will not receive routine care or will have current therapy stopped. $N\!/\!A$

**e. Justification for inclusion of a placebo or non-treatment group.** (see above background and design for purpose of saline placebo and blinding, respectively). There is no "non-treatment group" - both groups receive usual care - fentanyl. Blinding by pharmacy preparation of the drug and delivery system in identical, nondescript pump formats for both groups is standard in drug trials in order to prevent bias to confound prescription, observations, data recording, etc. There are actually 3-levels of blind in this project: Nurse at bedside, Patient/participant, and, research assistant.

**f. Definition of treatment failure or participant removal criteria.** Should a patient decide to withdraw, all efforts will be made to complete and report the observations as thoroughly as possible. Reasons for premature withdrawal may include:

- Disease progression
- Unacceptable adverse events.
- Intercurrent illness that prevents further administration of treatment or would affect assessment of clinical status to a significant degree.
- Initiation of non-protocol therapy for the disease under study.
- Non-compliance with protocol or treatment.
- Subject becomes pregnant.
- g. What happens to participants receiving therapy when study ends or if a participant's participation in the study ends prematurely

When the study ends or when a participant's participation ends prematurely, he/she will continue to receive usual care treatment.

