# Data Analysis Plan

[name], a professional biostatistician from the JH BEAD program specializing in clinical trials and longitudinal data analysis, had assisted Drs. [name] and [name] in conducting the statistical analyses in consultation with Going forward, this role will be assumed by biostatisticians at the JHU-ICTR.

The primary data analyses (Pain variables) will be conducted using analysis of covariance, or, longitudinal growth modeling (if normality assumptions are met) to examine group differences both in cross-section and longitudinally. If normality assumptions are violated then appropriate nonparametric tests will be utilized (e.g., Wald statistic). These methods allow for statistical controlling multiple potential confounding baseline variables and are robust against dropout - expected to be minimal. Data from the following study were used to generate this power estimate (Beaudoin, 2014).

Prior to study start-up, it is anticipated that, since ANCOVA is the recommended procedure for analyzing pre- to post- treatment change scores, that is the test that will be utilized for the primary aim, because: it is more powerful than t-test and Mann-Whitney; it can adjust for baseline group differences; it can be adjusted for baseline randomization strata; and, it can be utilized in analyzing repeated measures such as in the present study.

Prior to testing hypotheses, univariate distributions of variables will be inspected to assess normality, identify outliers, skewness or other abnormalities in distribution, determine appropriate summaries of location and spread and the need for transformation or nonparametric analysis. Preliminary analyses will determine whether the data meet basic assumptions for parametric tests. If relevant covariates are not balanced by the randomization, or confounds are distributed unevenly across groups, they will be included in the models as covariates.

If Pain Intensity is substantially associated with non-study factors (e.g., age, gender, TBSA) these variables will be statistically controlled as indicated in analyses.

The data on average (or summed) Opiate Sparing Effects from baseline to post-treatment, and within group and between group changes over time are likely not to meet criteria for parametric analysis, that is, they are expected to be non-normally distributed and thus inappropriate for Analysis of Covariance (ANCOVA).

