# **Participant Dropout**

Dropouts and participants whose wound care ends or changes substantially prior to the anticipated 7day study period will be handled on an intent-to-treat manner in all key analyses with the last data obtained treated as the endpoint for that participant. Reasons for dropout will be recorded and contrasted across group.

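### If the last-data rule is applied to the PTSD rate, a dropout with no 1-month assessment can only be scored as not PTSD, which biases the comparison towards the arm that loses more would-be cases

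*Combined protocol and SAP*

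**What the plan says.** All references are to the combined protocol and SAP.

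- **Definition.** The secondary-outcome list under Specific Aim #2 states: "By definition, to meet criteria for PTSD, symptoms must be present for 1 month". Before that point, "subjects with symptoms consistent with PTSD related to their burn injury will be diagnosed with ASD, rather than PTSD".
- **Hypothesis.** The same item predicts that the ketamine arm will have a "lower percentage of patients who meet criteria for PTSD, when compared to subjects in the UC group". This is PTSD alone, although the outcome is introduced as the rates of ASD and PTSD.
- **Visits.** Summary of Medication Dose, Timing, Method gives: "Follow-up 1 day, 1-week and 1-month after last of the 7-day study protocol for a total of 5 weeks". Treatment may last 3 to 7 days. Nothing is scheduled between 1 week and 1 month.
- **Missing data.** Participant Dropout covers dropouts and those whose wound care ends or changes early. They are handled "in all key analyses with the last data obtained treated as the endpoint for that participant". The term key analyses is not defined, and no other missing-data rule, model or sensitivity analysis is given for PTSD.
- **Expected loss.** The Data Analysis Plan says its methods "are robust against dropout - expected to be minimal". No dropout rate and no PTSD rate are stated.

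**The concern.** Carrying forward the last value normally keeps an earlier reading of the same measure. Here the earlier reading cannot take the value of interest. A participant last seen at 1 week with severe symptoms has ASD by definition, and carrying that forward to a PTSD-only endpoint gives not PTSD. Scoring the ASD as PTSD instead would contradict the protocol's own definition. The rule therefore does more than add noise: it fixes one answer for everyone it touches.

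At stake is the first-listed secondary outcome, which the Background presents as possible evidence of a preventive effect on PTSD. A difference in that rate could come partly from who was lost, and a real difference could be diluted. The primary pain analysis and its sample size are not affected by this point.

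**Working it through.** **1. Which visits can yield PTSD?** If the last study session is on study day 3 to 7, the 1-week visit falls on day 3 + 7 = 10 to 7 + 7 = 14. The 1-month visit falls on about day 3 + 28 = 31 to 7 + 30 = 37. For a 1-week visit on day 14 to be 28 days post-injury, treatment would have to start 28 − 14 = 14 days after the burn, whereas consent is sought as soon as possible after admission. Only the 1-month visit can yield the diagnosis.

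**2. Inputs.** The documents give no figure for PTSD prevalence or loss, so these are assumptions: true PTSD rate *p* of 20%, 30% or 40%, and loss before the 1-month assessment *d* of 10% to 30%. Arm size is taken as 47 from the corrected sample size estimate, which is for pain. That figure reproduces: difference 2.0 and SD 4.0 need 64 per arm by two-sided t-test at 80% power; the design effect is 1 + 10 × 0.7 = 8.0; and 64 × 8.0 / 11 = 46.5, so 47.

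**3. Bias formula.** If no one without a 1-month assessment can be positive, the bias in an arm is −(share lost × PTSD risk among those lost). When loss is unrelated to PTSD, this reduces to scored rate = *p* × (1 − *d*).

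**4. No true effect, loss unrelated to PTSD, 10% in one arm and 25% in the other.**

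| True rate, both arms | Arm losing 10% | Arm losing 25% | Spurious gap |
|---|---|---|---|
| 20% | 0.20 × 0.90 = 18.0% | 0.20 × 0.75 = 15.0% | 3.0 points |
| 30% | 0.30 × 0.90 = 27.0% | 0.30 × 0.75 = 22.5% | 4.5 points |
| 40% | 0.40 × 0.90 = 36.0% | 0.40 × 0.75 = 30.0% | 6.0 points |

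The gap favours whichever arm has the 25% loss. Reversing the loss reverses the sign.

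**5. Effect on false-positive risk.** With 47 per arm, a pooled two-proportion z-test at two-sided 0.05 (exact enumeration), a true rate of 30% in both arms and a more unequal loss of 30% v 10%, the scored rates are 21% v 27%. The chance of wrongly declaring the first arm lower is 9.9%, against 2.6% with no loss.

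**6. Equal loss.** With true rates of 20% v 40% and 20% loss in both arms, unrelated to PTSD, the scored rates are 16% v 32%. The difference shrinks from 20 to 16 points and power falls from 57% to 45%.

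**7. Does more dropout always win?** No. With loss of 20% v 10% and PTSD risk among those lost of 30% v 60%, the biases are −0.20 × 0.30 = −6 points and −0.10 × 0.60 = −6 points, and they cancel. With 30% v 70% they are −6 and −7 points, so the arm with less dropout gains.

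**The case against.** The strongest reply is that the rule may never reach this outcome, or may touch very few people.

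- **Scope.** Key analyses is undefined, and the rule's only time reference is the 7-day treatment period. It is unclear whether it covers a secondary diagnostic rate, or someone who completes treatment and then misses the 1-month visit. In a combined ASD and PTSD outcome, a carried-forward ASD diagnosis would count as a case. This stands, and it makes the point conditional. But the stated hypothesis is on PTSD alone, and if the rule does not apply, the plan has no missing-data rule for this outcome.
- **Follow-up.** Item 4f promises efforts to complete observations after withdrawal, and Real-Time Data Collection accepts telephone assessment. A participant who stops treatment early but is assessed at 1 month has a genuine outcome. This also stands. It reduces the number affected but does not say how a missing diagnosis is scored.
- **Size.** At 47 per arm, the 4.5-point artefact is about half a standard error: √[(0.27 × 0.73 + 0.225 × 0.775)/47] ≈ 8.9 points. If loss really is small, so is the bias.

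A reader might infer that the rule favours ketamine. The Background does report that "low-dose ketamine was associated with a higher risk of neurological (relative risk [RR] = 2.17) and psychological (RR = 13.86) events", and item 4f lists "Unacceptable adverse events" as a reason for withdrawal. But the same sentence of the Background reports more major cardiopulmonary events with opioids. Its review of four burn trials found no side effect that led to removal from study. Section 8, Risks, expects poorer pain relief under usual care, which could drive loss the other way. The Background also cites studies in both directions on ketamine and later PTSD symptoms. The documents do not settle which arm would lose more would-be cases.

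**Conclusion.** The concern holds in conditional form. If the last-data rule is applied to the PTSD-rate hypothesis, every dropout without a 1-month assessment is scored as not PTSD, whatever the symptoms. Each arm's rate is then too low by its share of such dropouts times their PTSD risk.

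Two stronger readings are not supported. One is that everyone who leaves early is counted as PTSD-free: those assessed at 1 month are not, and the reach of the rule is unclear. The other is that the arm with more dropout necessarily benefits: that needs similar PTSD risk among those lost in each arm, which the documents do not establish.

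Size and direction are unknown. The 3 to 6 point gaps rest on assumed PTSD rates of 20% to 40%, assumed loss of 10% v 25%, and loss unrelated to PTSD. The outcome is secondary and no power is stated for it, so this should be corrected but does not threaten the primary conclusion.

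**What to change.** 1. State in Participant Dropout that the last-data rule does not apply to the 1-month PTSD diagnosis, and define key analyses.
2. Treat a missing 1-month diagnosis as missing. Analyse it with a likelihood-based or multiple-imputation method that includes arm and earlier ASD severity.
3. Add a sensitivity analysis that counts dropouts with ASD at their last assessment as PTSD.
4. State that the completion effort in item 4f and the telephone option in Real-Time Data Collection cover the 1-month assessment for all randomized participants, including those who stopped treatment early.

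If loss is unrelated to PTSD, treating the diagnosis as missing returns each arm's expected rate to its true value: 30% v 30% in the illustration, instead of 27.0% v 22.5%. If loss depends on symptoms, the earlier ASD severity carries much of the correction, and the sensitivity analysis shows how far the result depends on it.

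The cost is a few sentences of protocol and SAP wording, a little more analysis work, and slightly wider intervals. The follow-up effort is largely promised already.

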# Trajectory, and, Mediator / Moderator Analyses

Finally, analyses will be conducted that take into account the variability of participant's responses over time. It is anticipated that these analyses may yield significant insight into patterns of Time and Time-by-Group responses that are not easily disentangled using traditional statistical methods. Thus, statistical analyses will include methods (e.g., latent growth mixture modeling, latent class growth curve analysis) to identify classes of patients with similar trajectories and mediator/moderator variables that effect outcome (e.g., stability, resilience, impairment). It is anticipated that these methods will enable identification of participants at greater or lesser risk for chronic pain and ongoing psychological distress. The potential impact on the quality of care, soldier safety and comfort, and early identification and risk stratification – possibly under austere battlefield conditions during the first painful procedures – cannot be over-estimated.

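### Catastrophizing and pain-anxiety scores taken after dosing has begun are planned as moderators of the drug effect; for catastrophizing, 6 or 12 of the 14 outcome sessions are already over

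*Combined protocol and SAP*

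**What the plan says.** The relevant text is in section 2, Objectives, in the list of secondary outcome measures that follows Specific Aim #2.

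- Catastrophizing (item 5): the moderator is "pain-related catastrophizing assessed within 1 hour prior to start of Day 1 (Session 1), Day 4 (Session 7) and Day 7 (Session 13"). It "will moderate the effect of Study Drug on measures of acute pain (across all 7 days and 14 sessions", and also "as well as during Sessions 1, 7 and 13 respectively".
- Pain anxiety (item 4): "pain anxiety assessed within 1 hour prior to start of Sessions 1, 5 and 7 will moderate the effect of Study Drug" on acute pain. No outcome window is given. A further hypothesis is that "change in pain anxiety will moderate the effect of study drug on change in PTSD symptoms and PTSD diagnosis".
- Expected drug effect on the two measures: ketamine "will result in significantly fewer symptoms of pain-related anxiety at 1-month follow-up" and "will result in significantly fewer symptoms of pain-related catastrophizing at 1-month follow-up".
- Method (section 7, Trajectory, and, Mediator / Moderator Analyses): "statistical analyses will include methods (e.g., latent growth mixture modeling, latent class growth curve analysis"). Mediators and moderators are named together. Nothing limits moderators to baseline values or late scores to later outcomes.

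**The concern.** A moderator of a randomized effect should be fixed before treatment, so that patients who share a value are still comparable between arms. Only the Session 1 score is of that kind. The later scores have two separate faults.

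1. **Time order.** A score taken on Day 4 or Day 7 cannot alter the drug's effect on sessions that are already over, yet the catastrophizing hypothesis covers all 14.
2. **Conditioning on a post-randomization variable.** The late scores follow several doses and several painful sessions. If either affects the score, ketamine and control patients with the same late score are different kinds of patient, and the arm contrast within that stratum is no longer randomized.

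At stake are the secondary statements about who benefits from ketamine, and any drug effect reported within high or low scorers.

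**Working it through.** **Inputs from the documents.** Score times and outcome windows: section 2, items 4 and 5. Target difference 2.0 points; SD 3.0 with 14 sessions or SD 4.0 with 11; intraclass correlation 0.7; design effects 10.1 and 8.0; 80% power at 0.05: section 4, sample size estimates 1 and 2. Arm sizes of 37 to 47: section 7.

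**Inputs assumed.** Within-arm correlation of late score with pain (0.3, 0.5, 0.7), and the strength of the link from earlier pain to the late score. The plan gives neither.

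**Step 1: the plan's own figure.** There is none for the moderator analyses. The primary sample size reproduces with a two-sample t-test (two-sided 0.05, 80% power), multiplied by the design effect and divided by the number of sessions:
- SD 3: 37 × 10.1 / 14 = 26.7, so 27 per arm, as stated.
- SD 4: 64 × 8.0 / 11 = 46.5, so 47 per arm, as stated.

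**Step 2: time order, at two sessions a day.**

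| Score taken before | Day | Sessions already over, of 14 |
|---|---|---|
| Session 1 | 1 | 0 |
| Session 5 (pain anxiety) | 3 | 4 (29%) |
| Session 7 (both) | 4 | 6 (43%) |
| Session 13 (catastrophizing) | 7 | 12 (86%) |

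**Step 3: drug effect at a given late score.** Let D = −2.0 be the true effect on pain, ρ the within-arm correlation of score with pain, and d the drug's effect on the mean score. In a linear model without true moderation:

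adjusted effect = D − ρ × (SD of pain / SD of score) × d

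If the drug moves the score only through pain, d = ρ × (SD of score / SD of pain) × D. The SDs cancel, leaving D × (1 − ρ²):
- ρ = 0.3: 2.0 × 0.91 = 1.82 points (9% lost)
- ρ = 0.5: 2.0 × 0.75 = 1.50 points (25% lost)
- ρ = 0.7: 2.0 × 0.51 = 1.02 points (49% lost)

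If d = 0, the adjusted effect is D and nothing is lost.

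**Step 4: simulation on the trial's layout.** 14 sessions, intraclass correlation 0.7, true effect −2.0, no true moderation, 37 or 47 per arm, 2,000 runs per case. Model: pain on arm, score and arm × score. The assumed link is in SDs of baseline catastrophizing per NAS point of earlier pain.

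| Score used | Link | Drug effect at mean score, SD 3 | SD 4 |
|---|---|---|---|
| Session 1 | any | −2.0 | −2.0 |
| Session 13 | 0.15 | −1.8 | −1.7 |
| Session 13 | 0.3 | −1.4 | −1.1 |
| Session 13 | 0.5 | −0.9 | −0.6 |

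The Session 7 score behaves almost identically.

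**Step 5: the interaction test.** With the same link in both arms, the error rate stayed at about 5% or below for early and late scores alike. With a link of 0.5 in control and 0.1 in ketamine (assumed), the late scores gave false moderation in 45% to 50% of runs, while the Session 1 score stayed at about 5%. The exact figures in steps 4 and 5 shift with the assumed noise in the score; the pattern does not.

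**The case against.** The strongest reply has four parts.

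- **The framework is partly there.** Section 4 (Statistical and Database Management Resource) foresees multilevel analysis of time-varying and time-invariant data, section 7 plans mediator as well as moderator analyses, and item 5 pairs scores with Sessions 1, 7 and 13. This stands in part: the paired analyses are in time order. But they still condition on a post-randomization score at Sessions 7 and 13, the pairing does not govern the 14-session clause, and no lag or baseline rule is stated.
- **Shrinkage is not false moderation.** The hypotheses concern an interaction, while step 3 concerns the drug effect at a given score. This stands. A reader might infer that the moderation tests must be wrong; step 5 shows that they can be, when the link differs by arm, and otherwise hold close to nominal error.
- **The plan does not say that ketamine lowers the in-week scores.** A reader might infer this from items 4 and 5, but both hypotheses are set at 1-month follow-up. An in-week effect is plausible, and remains an inference.
- **Pain anxiety differs from catastrophizing.** A reader might carry Day 7 and the 14-session window over to pain anxiety. By the plan's numbering its last score for this purpose is before Session 7, on Day 4, and its outcome window is unstated.

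**Conclusion.** The point holds for the late scores. Catastrophizing before Sessions 7 and 13 is out of time order for 6 and 12 of the 14 sessions whose drug effect it is said to moderate; this needs no assumption. Those scores, pain anxiety before Sessions 5 and 7, and change in pain anxiety are all post-randomization.

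The size of any bias depends on assumptions that the documents cannot settle. For a true 2.0-point effect, the loss in the drug effect at a given late score runs from zero (drug does not move the score) through 9%, 25% and 49% (drug moves it only through pain, correlation 0.3, 0.5, 0.7). False moderation is a risk only where the pain-to-score link differs between arms.

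A reader might infer that the randomized comparison as a whole is compromised. The documents do not support that: both primary aims, the 1-month arm comparisons and the Session 1 moderator analysis do not condition on these scores.

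**What to change.** In secondary hypotheses 4 and 5:

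- Name only the score taken before the first dose (Session 1) as moderator of the drug effect. Say that it is completed before the loading dose: the stated window is the hour before the session, and the loading dose starts about 10 minutes before wound care.
- Analyse the later scores and the change in pain anxiety as outcomes or mediators, or as lagged time-varying predictors of later sessions only. State that they are not read as moderation of the randomized effect.
- State the outcome window for the pain-anxiety hypothesis.
- Carry the same distinction into the trajectory and mediator/moderator paragraph of section 7.

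The cost is rewording and the loss of a few planned exploratory moderator analyses. No new data and no change in sample size are needed.
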